**Clinical Note to File, Form for ALXN-SOP-0005179**

Document Number	Version	Status	Effective Date
ALXN-FRM-0007589	2.0	Effective	03 Sep 2021

**CLINICAL NOTE TO FILE**

Protocol Number:	ALXN1210-ALS-308	
Site Number:	NA	Subject Number: NA
Re:	Interim Analysis Plan Version 3.0	
FILE (Check at least one)		
Sponsor Trial Master File: 	Investigator Site File: 	Other:  Please specify:

**Note to File:**

Two unblinded interim analyses were planned to be conducted during the Randomized-Controlled Period. Prior to study termination, the protocol was amended (23 Jun 2021, Amendment 6) to include only 1 interim analysis, and the Interim Analysis Plan was updated accordingly (02 Jul 2021, Version 3.0). Subsequently, Amendment 6 was never implemented in the study.

The interim analysis was conducted according to the ALXN1210-ALS-308 Interim Analysis Plan V3.0 and in alignment with the protocol version that was in effect at investigative sites at the time of the analysis (15 Oct 2020, Amendment 5).

Form – Source Copy

**Clinical Note to File, Form for ALXN-SOP-0005179**

Document Number	Version	Status	Effective Date
ALXN-FRM-0007589	2.0	Effective	03 Sep 2021

**REVISION HISTORY**

Version No.	Change Type (New, Revise, or Admin)	Revision Summary	Justification
2.0	Revise	Reclassifying to Form/Template Source copy as per DOQs Form/Template project	As per Change Control PR#107515

## VERSION HISTORY

This statistical analysis plan (SAP) for study ALXN1210-ALS-308 is based on protocol amendment 6 dated 23Jun2021.

SAP Version	Version Date	Change	Rationale
1	2July2021	Not Applicable	Original version
2	18Nov2021	See Section 6.4 (Appendix 4) for detailed changes.	Due to the study meeting the pre-specified futility criterion during the first interim analysis conducted by IDMC, the scope of the analyses for this study has been revised and is reflected in this SAP amendment

## 1. INTRODUCTION

This statistical analysis plan (SAP) describes the statistical methods for analyzing data for the study ALXN1210-ALS-308, “A Phase 3, Double-Blind, Randomized, Placebo-Controlled, Parallel-Group, Multicenter Study With an Open-Label Extension to Evaluate the Efficacy and Safety of Ravulizumab in Patients With Amyotrophic Lateral Sclerosis (ALS)”.

The scope of the analyses for this study has been revised and is reflected in this SAP amendment due to the study meeting the prespecified futility criterion. This SAP amendment will be finalized prior to the final database lock. No separate SAP will be developed for the Open-Label Extension (OLE) Period of the study.

The table, figure, and listing specifications will be provided in a separate data presentation plan document.

### 1.1. Objectives, Estimands and/or Endpoints

Objective	Estimand/Endpoint
Primary	
To evaluate the effect of ravulizumab compared with placebo on amyotrophic lateral sclerosis functional rating scale-revised (ALSFRS-R) score in adult patients with ALS	Estimand: Difference in mean combined assessment of function and survival (CAFS) score between ravulizumab and placebo in the eligible ALS patient population after accounting for the intercurrent event (ICE) of death into the CAFS score calculation using the composite strategy. See Section 5.3 for details.
Secondary	
To evaluate the effect of ravulizumab compared with placebo on ventilation assistance-free survival (VAFS) in adult patients with ALS	Estimand: Hazard ratio (ravulizumab versus placebo) of VAFS event in the eligible ALS patient population using treatment-policy strategy
To evaluate the effect of ravulizumab compared with placebo on respiratory function in adult patients with ALS	Estimand: Difference in mean change in slow vital capacity (SVC) percent predicted score between ravulizumab and placebo at Week 50 in the eligible ALS patient population using treatment-policy strategy
To evaluate the safety of ravulizumab compared with placebo in adult patients with ALS	Endpoint: Incidence of treatment-emergent adverse events (TEAEs), treatment-emergent serious adverse events (TESAEs), and TEAEs leading to study drug discontinuation
To evaluate the effect of ravulizumab compared with placebo on muscle strength in adult patients with ALS	Endpoint: Percent change in combined muscle megascore from Baseline at Week 50 as assessed by handheld dynamometry (HHD)
To evaluate the effect of ravulizumab compared with placebo on neurofilament light chain (NfL) concentrations in adult patients with ALS	Endpoint: NfL concentrations in serum at Week 50
To characterize the pharmacokinetics (PK) of ravulizumab in adult patients with ALS	Endpoint: Change in serum ravulizumab concentration over the study duration
To characterize the pharmacodynamics (PD) of ravulizumab in adult patients with ALS	Endpoint: Change in serum-free complement component 5 (C5) concentration over the study duration
To characterize the immunogenicity of ravulizumab in adult patients with ALS	Endpoint: Presence and titer of anti-drug antibodies (ADAs)

Objective	Estimand/Endpoint
Exploratory	
To evaluate the effect of ravulizumab compared with placebo on respiratory function in adult patients with ALS	Endpoint: Time to the first instance of SVC < 50% predicted during the 50-week Randomized Controlled Period (RCP)
To evaluate the effect of ravulizumab compared with placebo on overall health-related quality of life in adult patients with ALS	Endpoint: Change from Baseline in Short-Form Health Survey (SF-36) at Week 50; Change from Baseline in European Quality of Life Health 5-item questionnaire (EQ-5D-5L) at Week 50
To evaluate the safety of ravulizumab compared with placebo in adult patients with ALS	Endpoint: Shifts from Baseline in Columbia-Suicide Severity Rating Scale (C-SSRS) at Week 50; Change from Baseline in vital signs, electrocardiogram (ECG) parameters, and clinical laboratory assessments
To characterize biomarkers in adult patients with ALS	Endpoint: Change from Baseline in levels of biomarkers of complement dysregulation, neuroinflammation, and neurodegeneration
To evaluate the effect of ravulizumab compared with placebo on ALS-related health quality of life in adult patients with ALS	Endpoint: Change from Baseline in ALS assessment questionnaire (ALSAQ-40) score at Week 50
To characterize the effect of ravulizumab compared to placebo on disease stage in adult patients with ALS	Endpoint: Any increase from the baseline stage on the King's staging system (KSS) at Week 50
To evaluate the long-term efficacy of ravulizumab in adult patients with ALS	Endpoint: Change in ALSFRS-R total score, VAFS, SVC, HHD, and patient-reported outcome measures over time in all patients exposed to ravulizumab during the OLE Period
To evaluate the long-term safety of ravulizumab in adult patients with ALS	Endpoint: Incidence of TEAEs, TESAEs, and TEAEs leading to study drug discontinuation during the OLE Period

## 1.2. Study Design

Study ALXN1210-ALS-308 is a Phase 3, double-blind, randomized, placebo-controlled, parallel-group, multicenter study with an OLE to evaluate the efficacy and safety of ravulizumab in adult patients with amyotrophic lateral sclerosis (ALS). There are 3 periods in this study:

**Screening Period:** Patients will be screened for eligibility for up to 4 weeks during the Screening Period. Patients who are not taking or who are on a stable riluzole and/or edaravone regimen at Screening will be considered for participation.

**RCP:** Eligible adult ALS patients will be randomized in a 2:1 ratio to ravulizumab or placebo arm within each stratum as defined in [Table 1](#). Approximately 354 patients will be enrolled in North America, Europe, and the Asia-Pacific region. Weight-based intravenous infusion of ravulizumab or matching placebo will be administered in a blinded fashion until Week 42 during the RCP. The primary endpoint will be evaluated at Week 50.

**Table 1: Randomization Strata**

Strata	ALS Muscle Weakness at the Onset	Background ALS Therapy (Riluzole or Edaravone) at Study Entry	
	(Bulbar vs. Not)	On Stable Riluzole	On Stable Edaravone
1	Not bulbar	No	Yes, No
2	Not bulbar	Yes	Yes
3	Not bulbar	Yes	No
4	Bulbar	No	Yes, No
5	Bulbar	Yes	Yes
6	Bulbar	Yes	No

a Stable riluzole: at least 30 days on riluzole prior to Day 1.

b Stable edaravone: at least 60 days on edaravone prior to Day 1.

Abbreviations: ALS = amyotrophic lateral sclerosis; vs = versus

Patients who do not enter the study on riluzole and/or edaravone will not be permitted to start treatment with either drug during the RCP.

[figure not shown]
One unblinded interim analysis for futility is planned when approximately 33% of originally planned patients (N = 354) complete the Week 26 visit for the RCP. An independent data monitoring committee (IDMC) will be established to conduct this unblinded interim analysis and periodic review of accumulating data for patient safety and efficacy during the study. Details of the interim analysis methods are described in a separate interim analysis plan (IAP).

**OLE Period:** For each participant, the RCP ends, and the OLE Period starts, when the participant has completed the Week 50 visit assessments and received the first dose for the OLE. Regardless of the randomized assignment, all patients will receive ravulizumab during the OLE Period. Blind to the randomized treatment assignment will be maintained for patients and providers during the OLE Period until the end of the study. Initiation of riluzole and/or edaravone is permitted during the OLE Period. The first dose of the OLE Period will be administered in a blinded fashion to accommodate the loading dose for the patients originally randomized to placebo (see protocol for further details).

The OLE Period will continue for up to 2 years or until ravulizumab is approved and/or available (per country-specific regulations), whichever occurs first.

After the End of Treatment Visit or early discontinuation, patients will be followed for an additional 8 weeks after their last dose of the study drug.

**Figure 1: Study Design Schematic**

## 2. STATISTICAL HYPOTHESES

### 2.1. Primary Hypothesis

The primary null hypothesis is that the effect of ravulizumab is no different from placebo in functional decline measured by the change from Baseline in ALSFRS-R total score at Week 50. The alternative hypothesis is that ravulizumab will slow the disease progression by reducing the decline from Baseline in ALSFRS-R total score at Week 50 compared to placebo.

### 2.2. Secondary Hypotheses

The null hypotheses associated with the secondary objectives are that ravulizumab is no different from placebo for the respective endpoints; the alternative hypotheses are described below:

#### 2.2.1. Key Secondary Hypotheses

- **Time to VAFS:** The alternative hypothesis is that treatment with ravulizumab will prolong the time to VAFS compared to placebo.
- **Change in SVC percent predicted:** The alternative hypothesis is that treatment with ravulizumab will slow the decline from Baseline in SVC at Week 50 compared to placebo.

#### 2.2.2. Supportive Secondary Hypotheses

- **Change in muscle strength (HHD):** The alternative hypothesis is that treatment with ravulizumab will slow the decline from Baseline in muscle strength at Week 50 compared to placebo.
- **Neurofilament concentration (NfL):** The alternative hypothesis is that treatment with ravulizumab will reduce the NfL concentration level at Week 50 compared to placebo.

### 2.3. Tertiary Hypotheses

- **Change in SF-36:** The alternative hypothesis is that treatment with ravulizumab will reduce the worsening from Baseline in SF-36 physical component summary (PCS) and mental component summary (MCS) at Week 50 compared to placebo.

- **Change in EQ-5D-5L:** The alternative hypothesis is that treatment with ravulizumab will reduce the worsening from Baseline in EQ-5D-5L visual analog scale (VAS) and Health Stage Index at Week 50 compared to placebo.
- **Time to the first instance of SVC percent predicted < 50:** The alternative hypothesis is that treatment with ravulizumab will prolong the time to the first instance of SVC percent predicted < 50 compared to placebo.
- **Change in ALSAQ-40 score:** The alternative hypothesis is that treatment with ravulizumab will reduce the worsening from Baseline in ALSAQ-40 at Week 50 compared to placebo.
- **Change in KSS:** The alternative hypothesis is that treatment with ravulizumab will reduce the worsening in KSS at Week 50 compared to placebo.

### 3. SAMPLE SIZE DETERMINATION

The sample size calculations were based on information extracted from the PRO-ACT (Pooled Resource Open-Access ALS Clinical Trials) database consisting of clinical trials data pooled from 23 Phase 2/3 ALS clinical trials. Approximately 354 patients will be randomized to ravulizumab or placebo in a 2:1 ratio.

The mean change in ALSFRS-R total score in the placebo arm at Week 50 is estimated as -14.3 (assuming a monthly linear slope of the decline of 1.19 calculated based on the proposed study inclusion criteria). Assuming a 30% relative reduction in the monthly slope in the ravulizumab group is considered a clinically meaningful treatment effect (Castrillo-Viguera, 2010; Writing Group for Edaravone ALS Study., 2017), the mean change in ALSFRS-R total score at Week 50 is estimated as -10. A common standard deviation (SD) of 10.3 was estimated for the change from Baseline in ALSFRS-R total score. A total of 282 patients will be required to ensure at least 90% nominal power based on a 2-sided t-test (Type I error = 0.05) for detecting a non-zero treatment effect for ALSFRS-R (defined as the difference between ravulizumab and placebo in the mean change from Baseline in ALSFRS-R total score at Week 50). The total sample size is estimated as 354 after adjusting for a 20% dropout (Cudkowicz, 2013). Furthermore, assuming approximately 82% 1-year survival rate for placebo group and 50% relative reduction in the HR for mortality due to treatment with ravulizumab, this sample size will provide at least 90% nominal power based on the primary analysis (CAFS).

### 4. ANALYSIS SETS

**Table 2: Analysis Sets**

Analysis Set	Description
Screened Set	All consented participants
Randomized Set	All randomized participants grouped by randomized treatment group (for reporting disposition, demographics, and baseline characteristics)
SS	All participants who received at least 1 dose of the study drug (ravulizumab or placebo) in RCP. Participants will be compared for safety according to the treatment they actually received. For a participant to be analyzed according to the treatment they actually received and not according to the randomization schedule, they would have to receive that treatment for the entire duration of the RCP.

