#### **8.1.4.1. Randomized Controlled Period**

The Randomized Controlled Period is a double-blind, randomized, placebo-controlled period. Eligible patients will be randomized 2:1 to receive blinded doses of ravulizumab or placebo during the Randomized Controlled Period (Day 1 through Week 42).

- Patients in the ravulizumab group will receive a blinded loading dose of ravulizumab on Day 1, followed by a blinded maintenance dose on at Week 2 (Table 6), then once q8w up to Week 42 (inclusive) (Table 6).
- Patients in the placebo group will receive a blinded matching placebo dose via IV infusion on Day 1, followed by a blinded matching placebo maintenance dose at Week 2, then q8w up to Week 42 (inclusive).

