**Table 8: Analysis Sets**

Population	Description
Randomized Set	All randomized patients grouped by randomized treatment group (for reporting disposition, demographics, and baseline characteristics)
Full Analysis Set (FAS)	All randomized patients who receive at least 1 dose of study drug grouped by randomized treatment group (for reporting efficacy data)
Per Protocol Set	All randomized patients who receive at least 1 dose of study drug and without any major protocol deviations.
Safety Set (SS)	All patients who receive at least 1 dose of study drug grouped by treatment actually received (for reporting exposure and safety data). For a patient to be analyzed according to the treatment they actually received and not according to the randomization schedule, they would have to receive that treatment for the entire duration of Randomized Controlled Period.
Pharmacokinetic Analysis Set (PKAS)	All patients who receive at least 1 dose of study drug and have at least 1 postdose pharmacokinetic sample
Open-label Extension Set	All patients who receive at least 1 dose of ravulizumab starting from Week 50 onward (for reporting all data from the Open-Label Extension Period)

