Total dose administered (mg)	RCP (SS)	Total dose administered	Sum of all doses in RCP. Note: Placebo kits will contribute to zero doses.
	OLE (OLES)	Total dose administered	Sum of all doses in OLE. Note: Placebo kits will contribute to zero doses.
Total infusion volume (mL)	RCP (SS)	Total infusion volume	Sum of all infusion volume in RCP.
	OLE (OLES)	Total infusion volume	Sum of all infusion volume in OLE.

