**Table 5: Definition of TEAEs**

TEAE (RCP)	TEAE (OLE)
For RCP participants entering the OLE, a TEAE will be defined as any AE with onset on or after the first dose of IP in the RCP up to and including the day prior to the first OLE dose.	A TEAE will be defined as any AE with onset on or after first dose of OLE.
For RCP participants not entering the OLE, TEAE will be defined as an AE with onset on or after the first RCP dose of IP.	

If the time of the AE onset is available, it will be used to determine the treatment emergence by comparing with the time of the first study drug infusion, ie, if the AE onset time is prior to the time of infusion, it will not be considered as treatment-emergent.

Abbreviations: AE = adverse event; IP = investigational product; OLE = Open-Label Extension; RCP = Randomized Controlled Period; TEAE = treatment-emergent adverse event

The incidence, toxicity, and relationship to IP will be summarized by the treatment group. Specific AEs will be counted once for each participant for calculating percentages (e.g., overall, SOC, PT). In addition, if the same AE occurs multiple times for a participant, the highest severity and relationship to IP observed will be reported. All TEAEs will be summarized overall and categorized by MedDRA SOC and PT. The ordering of SOC will be alphabetical, and the ordering for PT will be most prevalent (using percentage) PT within each SOC based on the ravulizumab (RCP analysis) or total column (OLE). PTs with the same number of participants (eg, to break ties) will be further sorted by the number of events and then alphabetically.

Table 6 provides an overview of the tabular summaries of AEs for different periods, underlying analysis sets, and treatment group display convention. An “X” in the table represents that an analysis will be performed for the period. For incidence tables, the number of participants and percentage will be tabulated; percentages will be based on the number of participants in the respective treatment groups. For event-rate tables, the rate per 100 patient-years will be calculated as follows (see Table 4 for the definition of patient-years):

$$= 100 \times \frac{\text{Total number of TEAEs for specific reporting period}}{\text{Total Person years for specific reporting period}}$$

The following participant-level listings will be generated for AE data:

- All AEs
- All SAEs
- AEs leading to study drug discontinuation
- AEs leading to death
- AEs of special interest

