**Table 6: Overview of Adverse Event Analysis by Study Period**

Type of Analysis	Period Analysis Set Treatment Group Display Convention			Additional Notes
	Screening SS Ravulizumab, Placebo, Total	RCP SS Ravulizumab, Placebo	OLE OLES Ravulizumab/Ravulizumab, Placebo/Ravulizumab, Total	
Overall summary of TEAEs		X	X	
TEAEs by SOC and PT		X	X	
TESAEs by SOC and PT		X	X	
Nonserious TEAEs by SOC and PT		X	X	
TEAEs leading to study drug withdrawal by SOC and PT		X	X	
TEAEs leading to death by SOC and PT		X	X	
TEAEs by SOC and PT by highest relationship to IP		X		Relationship to IP: related, not related
TEAEs by SOC, PT, and highest severity		X		Severity: Grade 1, 2, 3, 4, and 5
TEAEs (IP-related) by SOC, PT, and highest severity		X		
TEAEs (IP-related) by SOC and PT		X		
TESAEs (IP-related) by SOC and PT		X		
TESAEs by SOC, PT, and highest relationship to IP		X		Relationship to IP: related, not related
TEAEs (≥ 1%) by SOC and PT		X		≥ 1% in all participants
TEAEs by SOC sorted by decreasing frequency		X		Decreasing frequency by ravulizumab arm (RCP), all participants (OLE)
TEAEs by PT sorted by decreasing frequency		X		
TESAEs by PT sorted by decreasing frequency		X		

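### The Safety Set rule tabulates a placebo-randomised participant who received ravulizumab at only some RCP infusions under placebo; a one-sentence change would correct this, though it is unlikely to alter results

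*SAP*

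**What the plan says.** SAP Table 2 opens the Safety Set definition with a general principle: "Participants will be compared for safety according to the treatment they actually received". The next sentence makes it conditional. "For a participant to be analyzed according to the treatment they actually received and not according to the randomization schedule", it says, "they would have to receive that treatment for the entire duration of the RCP". A participant who does not meet the condition is therefore grouped as randomised. Protocol Table 8 sets the same condition: "they would have to receive that treatment for the entire duration of Randomized Controlled Period". The two documents agree on this point.

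SAP Table 6 runs the RCP adverse event tables on this set with two columns: "RCP SS Ravulizumab, Placebo". No column is provided for mixed exposure. SAP Section 6.4 records that the Ravulizumab Exposure Set was removed in version 2, so no remaining analysis set is built on exposure to ravulizumab during the RCP.

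**The concern.** A safety set grouped by treatment received should place adverse events alongside the drug that could have caused them. The condition does this only when the wrong treatment was given throughout. Where a placebo-randomised participant received ravulizumab at some infusions, for instance through a kit error, every RCP event in that participant is tabulated under placebo, including events after the active infusion.

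The rule is symmetric in form, because a ravulizumab-randomised participant given some placebo stays under ravulizumab. The unwelcome direction is placebo to ravulizumab, since events after active drug then raise the comparator's incidence and make the drug look safer. The event of most interest is meningococcal infection, which is the identified risk in Protocol Table 4 and the only adverse event of special interest (AESI) in Protocol Section 8.4.5. Efficacy inference is descriptive only after the futility stop (SAP Section 5.1), so the safety tables are among the main remaining outputs.

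**Working it through.** The plan gives no figure for this point. The check is a reading of the rule, with one piece of arithmetic for scale.

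1. **Infusions in the RCP.** Protocol Section 8.1.4.1 schedules Day 1, Week 2, then every 8 weeks to Week 42: Day 1 and Weeks 2, 10, 18, 26, 34 and 42. That is 2 + (42 − 2)/8 = 7 infusions.

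2. **Applying the condition to a placebo-randomised participant who attends all 7.**
   - Ravulizumab at 7 of 7: condition met, tabulated under ravulizumab.
   - Ravulizumab at 1 to 6 of 7: condition not met, tabulated under placebo with all RCP events.
   - Ravulizumab at 0 of 7: tabulated under placebo, correctly.

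3. **The planned Week 50 switch is not affected.** For participants entering the open-label extension (OLE), SAP Table 5 counts RCP events "up to and including the day prior to the first OLE dose". Events after the planned ravulizumab loading dose in placebo participants therefore fall in the OLE tables.

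4. **Scale.** With 354 planned participants at 2:1, the placebo group is 354/3 = 118 and the ravulizumab group 354 × 2/3 = 236, taking all randomised participants as dosed. If *m* placebo-randomised participants with partial ravulizumab exposure each have a given event, they contribute *m*/118 to placebo incidence:

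| Assumed *m* | Contribution to placebo incidence |
|---|---|
| 0 | 0 |
| 1 | 1/118 = 0.85 points |
| 2 | 2/118 = 1.7 points |
| 5 | 5/118 = 4.2 points |
| 10 | 10/118 = 8.5 points |

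The documents give no value for *m*. The range is an assumption.

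**The case against.** The strongest reply is that the rule is a deliberate tie-break for mixed exposure, stated identically in both documents, and that nothing shows it will ever be used. Randomisation is central through interactive response technology (Protocol Section 6.3.1), infusions are supervised (Section 6.4), and no mis-dosing is reported. This stands and limits the weight of the point.

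A case would also not be invisible. SAP Section 5.6.2 lists all adverse events, serious events and AESIs by participant. Section 6.1.3 lists all protocol deviations, with investigational product among the categories. Table 4 sums the milligrams given, with the remark "Note: Placebo kits will contribute to zero doses", so a cross-over would appear as a non-zero dose in the placebo column. This stands in part. These outputs allow a case to be traced, but the adverse event tables would still label it placebo. The deviations determined programmatically in Section 6.1.3 are low dosing compliance and incorrect stratification, not wrong treatment received.

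A reader might go further in two ways.

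- **Early stoppers.** One might infer that a placebo-randomised participant who received only ravulizumab and then died or stopped also stays under placebo, because the RCP was never completed. The documents do not settle this. SAP Table 4 lets a participant's last RCP day be the date of discontinuation or death, and measures the duration of the RCP to that day. On that basis the participant received ravulizumab for the whole of their own RCP and moves to the ravulizumab column. Table 2 does not say whether it uses this definition, so this is an ambiguity and not a demonstrated error.
- **A reversed AESI comparison.** One might note that a single meningococcal case would read 0/236 against 1/118 as written, and 1/237 (0.42%) against 0/117 if regrouped. This requires a dosing error, the infection in that same participant, and no other case in either group. With one event in total, any reassignment reverses the direction, so the example does not measure bias.

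**Conclusion.** The point holds for mixed exposure. As written, a placebo-randomised participant who received ravulizumab at some but not all of the 7 RCP infusions is tabulated under placebo, which conflicts with the set's stated aim of grouping by treatment received. The size is about 0.85 percentage points of placebo incidence per such participant with a given event, assuming planned enrolment and 2:1 allocation. The overall effect depends on how many such participants exist. The documents report none, and if there are none every table is unchanged. A reader should not infer that mis-dosing occurred, that the safety comparison is known to be biased, or that participants who stopped early are necessarily misplaced. The change is worth making because it is cheap and removes a rule that, whenever it is triggered, credits events after ravulizumab to placebo. No safety test or stopping decision depends on it, since SAP Section 5.6 makes the safety analyses descriptive.

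**What to change.** Before final database lock, replace the conditional sentence in SAP Table 2 with a rule to this effect: *participants given one or more infusions containing ravulizumab from Day 1 up to, but not including, the first OLE (Week 50) dose are analysed in the ravulizumab group; participants given only placebo in that interval are analysed in the placebo group.* The Week 50 dose must be excluded explicitly. SAP Section 1.2 ends the RCP only once the first OLE dose has been received, so a rule worded as any ravulizumab during the RCP could move every placebo participant who rolled over. The new wording also removes the ambiguity about participants who stopped early.

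Add one listing of participants whose Safety Set group differs from the randomised group, with the dates of the infusions concerned. Record the change, and the difference from Protocol Table 8, in SAP Section 6.4.

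The cost is one sentence, one listing and one entry in the change table. The downside is that a mis-dosed placebo participant's events and person-time before the first ravulizumab infusion also move to the ravulizumab column, which slightly affects the rates per 100 patient-years. The listing shows which events preceded exposure.
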